7.1.3 Disease Parameters

Measurable disease

Measurable disease is defined as lesions (or tumors) that can be accurately measured in at least one dimension (longest diameter to be recorded) with a minimum size of 10mm by CT scan (irrespective of scanner type) and MRI (no less than double the slice thickness and a minimum of 10mm), 10mm caliper measurement by clinical exam (when superficial), and/or 20mm by chest X-ray (if clearly defined and surrounded by aerated lung).

All tumor measurements will be recorded in millimeters or decimal fractions of centimeters. Previously irradiated lesions are considered non-measurable except in cases of documented progression of the lesion since the completion of radiation therapy.

Target lesions

All measurable lesions up to a maximum of 5 lesions total (and a maximum of two lesions per organ) representative of all involved organs should be identified as target lesions and recorded and measured at baseline. Target lesions will be selected on the basis of their size (lesions with the longest diameter) and their suitability for accurate repeated measurements (either by imaging techniques or clinically). A sum of the longest diameter (LD) for all target lesions will be calculated and reported as the baseline sum LD. The baseline sum LD will be used as reference by which to characterize the objective tumor response.

Non-target lesions

All other lesions (or sites of disease) including any measurable lesions over and above the 5 target lesions should be identified as non-target lesions and should also be recorded at baseline. It is possible to record multiple non-target lesions involving the same organ as a single item on the case record form (e.g. "multiple enlarged pelvic lymph nodes" or "multiple liver metastases"). Bone lesions may be measurable if ≥ 1 cm on MRI. Measurements of these lesions are not required, but the presence or absence of each will be noted throughout follow-up.

Non-measurable disease (Tumor Markers)

Non-measurable disease is all other lesions (or sites of disease), including small lesions (longest diameter < 20 mm with conventional techniques or < 10 mm using spiral CT scan). Leptomeningeal disease, ascites, pleural or pericardial effusion, inflammatory breast disease, lymphangitic involvement of skin or lung, abdominal masses/abdominal organomegaly identified by physical exam that is not measurable by reproducible imaging techniques are all non-measurable. (e.g., PSA, CA-125, CA19-9, CEA)

7.2.1 Methods for Evaluation of Measurable Disease

All measurements will be taken and recorded in metric notation using a ruler or calipers. All baseline evaluations will be performed as closely as possible to the beginning of treatment and never more than 28 days before the beginning of the treatment.

The same method of assessment and the same technique will be used to characterize each identified and reported lesion at baseline and during follow-up. Imaging-based evaluation is preferred to evaluation by clinical examination when both methods have been used to assess the antitumor effect of a treatment.

7.2.2 Clinical Lesions:

Lesions will only be considered measurable when they are superficial (e.g., skin nodules, palpable lymph nodes). For the case of skin lesions, documentation by color photography including a ruler to estimate the size of the lesion is recommended. If measured by calipers, measurements have to be confirmed by two independent health care professionals.

7.2.3 Chest X-ray:

Lesions on chest X-ray are acceptable as measurable lesions when they are clearly defined and surrounded by aerated lung. However, CT is preferable.

7.2.4 Conventional CT and MRI:

Imaging should be performed with cuts of 10 mm or less in slice thickness contiguously. Spiral CT should be performed using a 5 mm contiguous reconstruction algorithm. This applies to the chest, abdomen, and pelvis.

7.3 Response Criteria

Evaluation of Target Lesions

Complete Response (CR)

Disappearance of all target lesions, determined by two separate observations conducted not less than 4 weeks apart. Any pathological lymph nodes (whether target or non-target) must have reduction in short axis to <10 mm (the sum may not be "0" if there are target nodes). There can be no appearance of new lesions.

Partial Response (PR)

At least a 30% decrease in the sum of the longest diameter (LD) of target lesions, taking as reference the baseline sum LD. There can be no appearance of new lesions.

Progressive Disease (PD)

At least a 20% increase in the sum of the SLD of target lesions, taking as reference the smallest sum SLD recorded since the treatment started and minimum 5 mm increase over the nadir, or the appearance of one or more new lesions.

Stable Disease (SD)

Neither sufficient shrinkage to qualify for PR nor sufficient increase to qualify for PD, taking as reference the smallest sum LD since the treatment started.

Evaluation of Non-Target Lesions

Complete Response (CR)

Disappearance of all non-target lesions and normalization of tumor marker level. All lymph nodes must be non-pathological in size (< 10 mm short axis).

Incomplete Response/Stable Disease (SD)

Persistence of one or more non-target lesion(s) and/or maintenance of tumor marker level above the normal limits.

Progressive Disease (PD)

Appearance of one or more new lesions and/or unequivocal progression of existing non-target lesions.

Evaluation of Best Overall Response

The best overall response is the best response recorded from the start of the treatment until disease progression/recurrence (taking as reference for progressive disease the smallest measurements recorded since the treatment started). The patient's best response assignment will depend on the achievement of both measurement and confirmation criteria.

Table 7 Response Criteria

Target Lesions	Non-Target Lesions	New Lesions	Overall Response	Best Response for this Category Also Requires
CR	CR	No	CR	> 4 weeks confirmation
CR	Non-CR/ Non-PD	No	PR	> 4 weeks confirmation
PR	Non-PD	No	PR	
SD	Non-PD	No	SD	documented at least once > 4 weeks from baseline
PD	Any	Yes or No	PD	no prior SD, PR or CR
Any	PD*	Yes or No	PD	
Any	Any	Yes	PD	

* In exceptional circumstances, unequivocal progression in non-target lesions may be accepted as disease progression

Duration of Response

Duration of overall response

The duration of overall response is measured from the time measurement criteria are met for CR or PR (whichever is first recorded) until the first date that recurrent or progressive disease is objectively documented (taking as reference for progressive disease the smallest measurements recorded since the treatment started).

The duration of overall CR is measured from the time measurement criteria are first met for CR until the first date that recurrent disease is objectively documented.

Duration of stable disease

Stable disease is measured from the start of the treatment until the criteria for progression are met, taking as reference the smallest measurements recorded since the treatment started.

Progression-Free Survival

Progression-free survival (PFS) is defined as the duration of time from start of treatment to time of progression.

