In a two arm Phase II trial, we will explore concurrent and sequential EIP testing two principles: Sequential priming with optimal immune activation (Arm A) and concurrent priming with maximal dosing of both epigenetic and immune modulators (Arm B).

Figure 1. Schematic of dosing schedule

2 Objectives of the Study

2.1 Primary objective:

- To define the optimal approach for epigenetic immune priming in hormone refractory breast cancer on the basis of overall response rate (ORR: CR+PR+SD at 24 weeks).
- Safety and tolerability of vorinostat, tamoxifen and pembrolizumab

2.2 Secondary objectives:

- To define the optimal approach for epigenetic immune priming in hormone –resistant breast cancer and ER-negative tumors
- To assess duration of response (DOR) 24 week landmark progression free survival (PFS:24)
- Median PFS and overall survival (OS)

- d) Tumor responses will also be calculated by Immune Related Response-Criteria (irRC).
- e) To test the response of tumor PD-L1 expression to epigenetic modulation

2.3 Exploratory objectives:

- a) To assess for post-treatment changes in tumor-infiltrating lymphocyte (TIL) populations, PD-L1 expression and potential indicators of response. If tumor samples demonstrate that epigenetic therapy converts tumors from a low (baseline) to high TIL (post-treatment) but without a corresponding increase in ORR, then we can confidently reject our hypothesis that enhancing TILs will increase pembrolizumab efficacy in this tumor type.
- b) Acetylation of histones in PBMCs as a pharmacodynamics response marker for vorinostat.

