3.6 Randomization Procedures

This is an open-label randomized trial; therefore, the Sponsor, investigator and subject will know the treatment administered. Two arms will be tested, with each independent assessment. Patients will be randomized to either arm using a computerized randomization program by [name]. Patients will be further stratified by prior number of chemo- and hormonal therapies.

No randomization is required for ER-negative patients (patients must have biopsiable disease)

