8.3 Analyses Plans

8.3.1 Analysis Populations

We will conduct an intention-to-treat analysis of efficacy. All patients who were randomized will be evaluated.

For evaluation of safety, we will restrict the arm-specific samples to all patients who have received at least one dose of investigational therapy.

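### Duration of response and PFS end only at progression: death is not an event and no censoring rule is given, so read literally both secondary endpoints run too long

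*Combined protocol and SAP*

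**What the plan says.** All the relevant definitions stand at the end of Section 7.3, Response Criteria, of the combined protocol and SAP.

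- **Duration of overall response** runs from first CR or PR "until the first date that recurrent or progressive disease is objectively documented".
- **Duration of CR** runs "until the first date that recurrent disease is objectively documented".
- **Duration of stable disease** runs from start of treatment until the progression criteria are met.
- **PFS**: "Progression-free survival (PFS) is defined as the duration of time from start of treatment to time of progression".

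DOR, PFS at 24 weeks and median PFS are secondary objectives (Section 2.2) and secondary endpoints (Section 2.4.2). Section 8.3.2 gives an analysis method only for the response rate. No section gives an estimator or censoring rule for DOR or PFS.

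On the analysis set, Section 8.3.1 says: "We will conduct an intention-to-treat analysis of efficacy. All patients who were randomized will be evaluated". Section 3.6 adds, for Arm C: "No randomization is required for ER-negative patients".

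Section 6.2.2 follows patients for disease status until, among other things, progression or death. After progression or new therapy they are telephoned every 12 weeks for survival.

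**The concern.** An endpoint called progression-free survival normally fails at progression or death, whichever comes first. Here it fails only at progression. DOR has the same gap. A patient who dies before progression is documented has no end event under these definitions. If the analyst censors that patient at the last scan, the estimate treats the death as carrying no bad news, and the durations come out too long.

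Such deaths are plausible under this schedule. Restaging falls at weeks 9 and 18, then every 3 cycles, and after 6 months it may be spaced to every 6 cycles, or 6 × 3 = 18 weeks (Section 6.1). Off treatment it is every 12 weeks (Section 6.2.2). Section 3.4 also withdraws patients for clear clinical progression without radiographic confirmation, and Section 7.3 does not say whether that counts as objectively documented.

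A lesser matter is the PFS origin. A patient randomised but never treated belongs to the intention-to-treat set but has no PFS time zero.

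**Working it through.** **1. What the plan's own figures rest on.** The plan states no figure for DOR or PFS. Its design figures are alpha 0.0471 and power 80.5% per arm, for a response rate of 10% against 30%, stopping at 0 or 1 responses in 10, otherwise going on to 29 (Section 8.2). The final cut-off is not printed, so I tried several:

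P(success | p) = Σ over x = 2 to 10 of Bin(x; 10, p) × P(Bin(19, p) ≥ r + 1 − x)

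| r (success if more than r of 29) | p = 0.10 | p = 0.30 |
|---|---|---|
| 4 | 0.1016 | 0.8369 |
| 5 | 0.0471 | 0.8051 |
| 6 | 0.0177 | 0.7389 |

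With r = 5 both stated figures are reproduced. They depend only on the 24-week response rate. Redefining DOR or PFS changes none of them.

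**2. Effect of leaving out deaths.** Let f be the share of first events that are deaths without documented progression. The documents give no value for f, so the values below are assumptions. With constant hazards, total hazard λ and progression hazard (1 − f)λ:

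- median to progression or death = ln 2 / λ
- median with deaths censored = ln 2 / [(1 − f)λ]
- ratio = 1 / (1 − f)

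For f = 5%, 10% and 20% the ratio is 1/0.95 = 1.053, 1/0.90 = 1.111 and 1/0.80 = 1.25, so the median is longer by about 5%, 11% and 25%.

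**3. In months.** For scale I use two medians quoted in Section 1.3.1: a response duration of 10.3 months (vorinostat with tamoxifen) and a PFS of 4.3 months (entinostat with exemestane). Treating each as the true median to progression or death is an assumption. For the landmark, 24 weeks = 24 × 7 / 30.4375 = 5.52 months, and

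S(24 weeks) = exp[−ln 2 × (1 − f) × 5.52 / 4.3]

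| f | Median DOR, months | Median PFS, months | 24-week PFS |
|---|---|---|---|
| 0 (deaths counted) | 10.3 | 4.3 | 41.1% |
| 5% | 10.8 | 4.5 | 43.0% |
| 10% | 11.4 | 4.8 | 44.9% |
| 20% | 12.9 | 5.4 | 49.1% |

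**4. PFS origin.** Starting at first dose shortens each PFS time by the lag from randomisation. The lag is not given. Assumed lags of 3 to 28 days are 3/30.4375 = 0.1 to 28/30.4375 = 0.9 months. In Table 5.1 Arms A and B both receive vorinostat and tamoxifen in all cycles, so no difference in lag between them is expected. What remains is any patient randomised but never treated.

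**The case against.** The best reply is that the plan never says what happens to a patient who dies. A reader might infer that such a patient will be counted as still responding, or censored. Neither is stated, so the upward bias is a consequence of following the definition literally, not a declared method. That stands as a limit on the claim. It does not remove the defect: the end events are written down, death is not among them, and no other section adds it.

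Three stronger readings do not hold.

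- **Size from a single death.** With 6 to 9 responders per arm (19% to 30% of 29 is 5.5 to 8.7), one event is a Kaplan-Meier step of 1/9 to 1/6, or 11 to 17 percentage points. A reader might take this as the bias. It is only the height of one step, whatever caused the event. The upper count is also wrong for DOR: the 30% target includes stable disease, while DOR covers CR and PR only. The objective response rates of 19% and 6.3% quoted in Section 1.3.1 would give about 5.5 and 1.8 responders in 29.
- **Spill-over to the primary endpoint.** Section 8.2 counts stable disease lasting at least 24 weeks, so a reader might think a patient who died could still count as stable. Section 8.3.2 defines the primary endpoint by status at 24 weeks, and a dead patient does not have stable disease or better.
- **Breakdown of intention-to-treat.** The origin mismatch touches only randomised but untreated patients in Arms A and B, and their number is not given. Section 8.3.2 already uses the randomised denominator for the primary endpoint. Arms are assessed independently, and no test of PFS between arms is planned.

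It is also fair that DOR and PFS carry no hypothesis test and that DOR will be imprecise under any definition.

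**Conclusion.** The definitions are wrong as written for DOR and PFS. Followed literally, PFS is time to progression, and deaths without documented progression produce no event. If those deaths are censored, median DOR, median PFS and 24-week PFS are biased upward. The increase in the median is about 5%, 11% or 25% if 5%, 10% or 20% of first events are such deaths. These shares are assumed, and the calculation needs constant hazards. The direction is clear, but the documents cannot fix the size.

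The damage is confined to secondary estimates. The PFS origin is a minor alignment for Arms A and B, and Arm C needs an origin of its own because it is not randomised.

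**What to change.** 1. In Section 7.3, define DOR as first CR or PR to progression or death from any cause, whichever is first. Use the same rule for duration of CR, and for duration of stable disease if it is reported.
2. Define PFS, including the 24-week landmark, as ending at progression or death from any cause. Adding death to DOR alone would leave the two endpoints inconsistent.
3. State the censoring rules: patients alive without progression, new anti-cancer therapy (where Section 6.2.2 stops disease-status follow-up), missed scans before an event, and no scan after baseline. Say whether clinical progression without radiographic confirmation is an event.
4. For Arms A and B, either start PFS at randomisation or declare PFS a treated-set analysis. For Arm C, state registration or first dose as the origin.

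The cost is wording. Section 6.2.2 already follows patients to death, and randomisation is computerised (Section 3.6), so no new data collection should be needed. Reported durations may be somewhat shorter than under the present text. Sample size and the primary test stay as they are.

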7.4 Evaluation of Safety

Analyses will be performed for all patients having received at least one dose of study drug. The study will use the [CTCAE v4.0](#) for reporting of non-hematologic adverse events and modified criteria for hematologic adverse events, see Section 7.5.

For multicenter studies, the Principal Investigator at the UCSF Coordinating Center will hold the role of Study Chair. The Study Chair is responsible for the overall conduct of the study and for monitoring its safety and progress at all participating sites.

7.5 Adverse Events

7.5.1 Adverse Event (AE) Monitoring

The investigator or qualified designee will assess each subject to evaluate for potential new or worsening AEs as specified in the Trial Flow Chart and more frequently if clinically indicated. Adverse experiences will be graded and recorded throughout the study and during the follow-up period according to NCI CTCAE Version 4.0 (see Section 7.5). Toxicities will be characterized in terms regarding seriousness, causality, toxicity grading, and action taken with regard to trial treatment.

All AEs of unknown etiology associated with pembrolizumab exposure should be evaluated to determine if it is possibly an event of clinical interest (ECI) of a potentially immunologic etiology (irAE).

Please refer to section 7.5 for detailed information regarding the assessment and recording of AEs.

7.5.2 Definition of Adverse Event

An adverse event (also known as an adverse experience) is defined as any untoward medical occurrence associated with the use of a drug in humans, whether or not considered drug related. More specifically, an adverse event (can be any unfavorable and unintended sign (e.g., an abnormal laboratory finding), symptom, or disease temporally associated with the use of a drug, without any judgment about causality. An adverse event can arise from any use of the drug (e.g., off-label use, use in combination with another drug) and from any route of administration, formulation, or dose, including an overdose.

7.5.3 Adverse reaction

An adverse reaction is defined as any adverse event caused by the use of a drug. Adverse reactions are a subset of all suspected adverse reactions for which there is reason to conclude that the drug caused the event.

7.5.3.1 Suspected

A suspected adverse reaction is defined as any adverse event for which there is a reasonable possibility that the drug caused the adverse event. For the purposes of IND safety reporting, “reasonable possibility” indicates that there is evidence to suggest a causal relationship between the drug and the adverse event. A suspected adverse reaction implies a lesser degree of certainty about causality than an adverse reaction.

7.5.3.2 Unexpected

An adverse event or suspected adverse reaction is considered unexpected if it is not listed in the investigator brochure or package insert(s), or is not listed at the specificity or severity that has been observed, or, if an investigator brochure is not required or available, is not consistent with the risk information described in the general investigational plan or elsewhere in the current application.

“Unexpected,” as used in this definition, also refers to adverse events or suspected adverse reactions that are mentioned in the investigator brochure as occurring with a class of drugs or as anticipated from the pharmacological properties of the drug, but are not specifically mentioned as occurring with the particular drug under investigation.

Adverse events that would be anticipated to occur as part of the disease process are considered unexpected for the purposes of reporting because they would not be listed in the investigator brochure. For example, a certain number of non-acute deaths in a cancer trial would be anticipated as an outcome of the underlying disease, but such deaths would generally not be listed as a suspected adverse reaction in the investigator brochure.

Some adverse events are listed in the Investigator Brochure as occurring with the same class of drugs, or as anticipated from the pharmacological properties of the drug, even though they have not been observed with the drug under investigation. Such events would be considered unexpected until they have been observed with the drug under investigation. For example, although angioedema is anticipated to occur in some patients exposed to drugs in the ACE inhibitor class and angioedema would be described in the investigator brochure as a class effect, the first case of angioedema observed with the drug under investigation should be considered unexpected for reporting purposes.

7.5.3.3 Serious

An adverse event or suspected adverse reaction is considered serious if, in the view of either the study PI or Merck, it results in any of the following outcomes:

- Death
- Life-threatening adverse event
- Inpatient hospitalization or prolongation of existing hospitalization
- A persistent or significant incapacity or substantial disruption of the ability to conduct normal life function
- Congenital anomaly/birth defect

Important medical events that may not result in death, are life-threatening, or require hospitalization may be considered serious when, based upon appropriate medical judgment, they may jeopardize the patient or subject and may require medical or surgical intervention to prevent one of the outcomes listed in this definition. Examples of such medical events include allergic bronchospasm requiring intensive treatment in an emergency room or at home, blood dyscrasias or convulsions that do not result in inpatient hospitalization, or the development of drug dependency or drug abuse.

7.5.3.4 Life-threatening

An adverse event or suspected adverse reaction is considered life-threatening if, in the view of either the study PI or Merck, its occurrence places the patient or subject at immediate risk of death. It does not include an adverse event or suspected adverse reaction that, had it occurred in a more severe form, might have caused death.

